From recent meta-analysis, three dual-armed studies that compared embolization and conventional surgery groups and six single-armed case series were identified and analyzed. Hematoma recurrence rate was significantly lower in the embolization group compared to the conventional treatment group (2.1% vs 27.7%, OR .087, 95% CI .026-.292, $p<.001$, $I^2=0\%$), whereas surgical complication rates were similar between the two (2.1% vs 4.4%, OR 0.563, 95% CI 0.107-2.96, $p=.497$, $I^2=27.5\%$). Number of patients with mRS>2 in the embolization (12.5%) versus conventional treatment (9.1%) groups also showed no statistical difference ($p=.689$). A composite hematoma recurrence rate of 3.6% was found after summing the six-case series. Composite recurrence and complication rates in the embolization cohorts of the dual-armed studies as well as the case series were also lower than literature values for conventional surgical treatments. Since then, there has been one study with 60 embolizations showing a 90% success rate of avoiding subsequent surgery with no procedural-related complications.

Objective

Through the use of a prospective dual cohort, this study seeks to assess the safety and efficacy of middle meningeal artery embolization for subdural hematoma in addition to standard treatments, which include observation and surgical evacuation. Middle meningeal artery embolization has emerged recently as a minimally invasive and successful method of preventing re-accumulation of subdural hematoma, particularly for patients that are not obvious surgical candidates or those with recurrent or refractory hematomas. We will compare the outcomes of these two groups of patients who undergo middle meningeal artery embolization to matched historical controls from the past four years.

Specific Aim 1:

Determine the efficacy of middle meningeal artery embolization vs observation alone

The recurrence rate of patients that undergo the middle meningeal artery procedure will be compared to a number of medically managed patients that experience a clinically significant persistent or recurrent hematoma. This endpoint will be determined through a series of neurologic assessments and follow up imaging. Patients will be followed for 90 days.

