Secondarily, the number of patients in each treatment group that experience persistence or recurrence to the degree that surgical evacuation is required will be compared. Patients who prospectively undergo middle meningeal artery embolization will be compared to retrospective matched controls of patients that underwent medical management. We hypothesize that patients who undergo MMA embolization as compared to simple observation alone will be less likely to ultimately need surgery and have a higher likelihood of SDH resolution after 90 days.

Specific Aim 2:

Determine the safety and efficacy of middle meningeal artery embolization for recurrent and refractory subdural hematomas after initial surgical evacuation.

MMA embolization has emerged as an adjunct treatment for patients who experience recurrent or refractory SDH after initial surgical evacuation. These patients will require surgical evacuation of the hematoma for their condition regardless of the use of MMA embolization. For patients with a residual SDH or who develop recurrent SDH within 30 days of initial standard of care surgery, the patients that have adjunct treatment with MMA embolization will be compared to historical patients that are managed with continued observation versus repeat surgery. We hypothesize that patients who undergo MMA embolization will have a higher likelihood of demonstrating radiographic improvement of the SDH and have a lower rate of requiring additional surgery.

Methodology

Participants

Approximately 200 patients with chronic subdural hematoma are treated at Barnes-Jewish Hospital annually. Patients aged 18+ of any race, sex, and socioeconomic status undergoing treatment for subdural hematoma will be identified by screening of the inpatient neurosurgical units or identification by an investigator. Patients will be approached regarding enrollment in the study at the time a decision is made to treat the subdural hematoma. If a patient expresses interest, an investigator or coordinator will provide the written consent form and explain the

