information gathered, time frame of participation, potential benefits, and risks of participation, including the risks of undergoing an interventional neuroradiology procedure. Treatment with middle meningeal artery embolization will be offered in addition to the standard surgical evacuation or observation by the physician in consideration of the patient's medical history and current condition. If patients are unable to provide informed consent, consent from the next of kin will be obtained in accordance with Missouri Statute Title XXVII, Section 431.064.

Patients will have as much time as they desire to think about the study, ask questions, and discuss with family. Any patient requiring emergent intervention or experiencing sudden neurologic deterioration is excluded from this study. The consent documentation contains a statement that consent is freely given, that the patient understands the potential risks and benefits of entering the study, and that the patient is free to withdraw from the study at any time. As the patient may experience a direct benefit from the study, the patient must initial yes/no to permission for future use of their data per policy. Patients who agree will then sign the IRB approved consent form prior to undergoing the procedure. The original signed consent will be maintained in a binder in a locked office. A copy will be given to the patient, with contact numbers if the patient has further questions or wishes to withdraw their consent. The expected duration of patient participation in the study is 90 days.

Based on a review of prior literature, we expect an effect size of 20% patients to meet the endpoint of recurrent or refractory subdural hematoma requiring surgery. With the addition of MMA embolization, we expect that only 5% of patients will meet this outcome. With equal numbers of patients in each arm, we estimate that 124 patients will be needed for a power of 80% using a two tailed alpha set at 0.5. In order to account for study dropout, we plan to study 200 patients who undergo MMA embolization. These patients will be compared to an additional 400 historical matched controls obtained via retrospective chart review from January 1st 2014 to December 31st 2018.

Inclusion/Exclusion Criteria

Must meet the following criteria for inclusion to undergo MMA embolization:

1. Patients 18 years or older undergoing treatment for a new diagnosis of chronic or acute subdural hematoma (cSDH)
or

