Patients 18 years or older who have undergone surgical evacuation of a subdural hematoma and have a significant residual hematoma status post-surgery or who develop a recurrent subdural hematoma.
2. Minimal symptoms such as headache, altered mental status, or mild neurological deficit only
3. Ability to understand and sign written informed consent by patient or LAR

If any of the following criteria are met, the individual will be excluded from participation:

1. Significant midline shift and/or neurologic symptoms requiring urgent decompression.
2. Common carotid stenosis of over 50%.
3. Significant contraindication to angiography (eg. kidney failure, difficult anatomy).

4. SDH related to underlying condition

Groups:

1. Embolization Only
 - a. Patients with new chronic or acute SDH with minimal symptoms only, or who are poor surgical candidates (dual antiplatelet therapy or systemic anticoagulation, ASA Class 4 or greater)
2. Embolization + Standard of Care Evacuation
 - a. Patients with chronic or acute SDH who failed conventional surgery at any point needing additional intervention, not requiring urgent evacuation
 - b. Recurrent SDH
3. Medical Management (Historical Cohort)
4. Surgery Alone (Historical Cohort)

Study Procedure

Middle meningeal artery embolization is ideal for patients with minimal symptoms or that are poor surgical candidates due to the need for continued anticoagulant or antiplatelet therapy. For patients who meet inclusion criteria, MMA embolization as an adjunct treatment will be offered. For patients that are medically managed, they will undergo MMA embolization to prevent growth or recurrence of the hematoma and have standard imaging follow up. For patients that require evacuation of the hematoma due to size or symptoms, they will undergo standard of care surgery via burr hole or craniotomy at the treating neurosurgeon's discretion and then at a later date during the same hospitalization receive MMA embolization. These patients may have already had multiple surgical evacuations with recurrence of the hematoma.

Once consented and enrolled, patients will undergo MMA embolization in the neuro-angiography suite via selective MMA catheterization and embolization with 150-250 micron polyvinyl alcohol (PVA) particles. The neurointerventional radiology department at BJH is a high volume center. Physicians and staff are experienced in neurovascular embolization for a variety of indications.

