The National Institutes of Health Stroke Scale (NIHSS) is an objective measure of impairment caused by a stroke. Eleven items are evaluated, with a potential score ranging from 0 to 42, with a higher score indicating more impairment.

Privacy/Data Protection

Patients will be assigned a unique study identification number at the time of consent. This number will link to identifying protected health information in a separate locked database accessible only to relevant research team members. Clinical study data will be entered into a secure database on RedCap under the study ID number to maintain patient data confidentiality.

Screening:

Study ID	MRN	Last Name	First Name	Admit Date	Enrolled Y/N	Date Consent Signed	Signed By Patient/ LAR	Exclusion

Initial Data:

Study ID	Birth Year	Sex	Race	(relevant comorbidities)	Use Anticoagulant y/n	Name of Med (aspirin, warfarin)	Procedure Date	Presenting neuro symptoms

Any neuro history	NIHSS Presentation	Baseline mRS	Size of SDH at Presentation	Laterality of SDH Left Right bilateral	Procedural Complications	

Follow up:

Study ID	Date of Follow Up	Time Point (30, 90 days)	NIHSS	mRS	Size of SDH at follow up	Neuro Deficit

Analysis

Endpoints

Two primary endpoints will be analyzed, related to the two main aims of the study. Aim 1 is to establish if middle meningeal artery embolization is more effective than observation alone at preventing recurrence of subdural hematoma. Aim 2 is to determine if adding on middle meningeal artery embolization reduces the need for further surgery in patients that initially undergo evacuation. The number of patients that experience a recurrent or refractory subdural hematoma will be compared, as well as the number of patients in each group that require surgery after undergoing embolization.

Primary Endpoints:

Recurrent or progressive SDH
Secondary surgical evacuation required

Secondary Endpoints:

Change in size of SDH at follow up
Procedure-related complications
New neuro deficit
NIHSS/mRS at follow-up intervals

Statistical Analysis

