Statistical comparisons will be made for the number of patients that experience a recurrent or refractory subdural hematoma, as well as the number of patients in each group that require evacuation surgery after undergoing embolization, an indication that the embolization procedure failed. These primary endpoints will be compared with simple t-test. The secondary endpoint of the change in the size of the subdural hematoma on radiographic imaging will be analyzed by repeated measures ANOVA. Change in score on NIH Stroke Scale pre and post embolization will be compared to determine the functional outcome of the procedure. For a safety analysis, the rate of procedure-related complications between embolized patients and surgical controls will be compared by t-test. Rankin Score at the follow up intervals will be compared with a Chi Square analysis.

Safety Monitoring Plan

Research will be performed according to protocols approved by the Institutional Review Board at Washington University in St. Louis School of Medicine. An application to the IRB is currently pending.

Patients with subdural hematoma present with symptoms including confusion or altered mental status, decreased consciousness, weakness or numbness on one side of the body, headache, seizure, and difficulty with speech, swallowing, or walking.

During this study, assessment of medical history and physical examination will be performed at baseline and at stated follow up intervals to ascertain neurologic status, change in functional baseline, and occurrence of any AEs. Prior to interventional procedures, patients have coagulation tests performed to assess risk of bleeding. If the patient has an allergy to iodinated contrast, they will receive standard pre-medication. During the embolization procedure, patients undergo continuous vital sign monitoring and are assessed frequently by a dedicated, ACLS-certified procedural nurse. The patient will be monitored as an inpatient in the neuroICU or stepdown unit for a minimum of 24-48 hours after the procedure.

Adverse Events

An adverse event (AE) is any untoward medical occurrence in a subject during participation in the clinical study or with use of the experimental agent being studied. An adverse finding can include a sign, symptom, abnormal assessment (laboratory test value, vital signs, electrocardiogram finding, etc.), or any combination of these.

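### In the evacuation cohort complications are tracked from embolization, so evacuation harm may count only in the surgical controls and the safety comparison can favour embolization

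*Combined protocol and SAP*

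**What the plan says.** **Comparison.** The Objective section states: "We will compare the outcomes of these two groups of patients who undergo middle meningeal artery embolization to matched historical controls". For safety, Statistical Analysis says that "the rate of procedure-related complications between embolized patients and surgical controls will be compared by t-test". Aim 2 names safety alongside efficacy.

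**Order of procedures.** For patients needing evacuation, Study Procedure has them operated on first and "then at a later date during the same hospitalization receive MMA embolization". Specific Aim 2 says of this population: "These patients will require surgical evacuation of the hematoma for their condition regardless of the use of MMA embolization".

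**Start of counting.** Study Procedure describes embolization and then has patients followed for 90 days after the procedure for complications. Exams fall before the procedure and at 30 and 90 days after it. Statistical Analysis says: "Change in score on NIH Stroke Scale pre and post embolization will be compared to determine the functional outcome of the procedure". There, the procedure means embolization.

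**Left open.** No index date or complication window is given for the surgery-alone historical cohort. Nothing says whether evacuation complications count as procedure-related in embolized patients. "New neuro deficit" appears under Secondary Endpoints with no reference exam, no time window and no named test.

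**The concern.** Group 2 patients and their surgical controls both undergo evacuation. If complications in Group 2 are counted from embolization, those of the preceding evacuation fall before the count begins. In the controls, surgery is the only procedure to which a complication can be attributed, so evacuation complications are what gets counted. The test then sets embolization harm against evacuation harm, although Group 2 carries both.

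The question for Aim 2 is what embolization adds to, or removes from, the harm of evacuation alone. A comparison built this way does not answer it, and could show the combined treatment as safer than one of its own components. Only the safety secondaries are at stake; the two primary endpoints are not touched by this point.

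**Working it through.** The document states no expected difference or power for the safety endpoints, so there is no planned figure to reproduce. The calculation is an illustration from the document's own rates.

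**Inputs**
- Embolization complications, e = 2.1% (Prior Research; Risks).
- Surgical complications, s = 4.4% (Prior Research: "surgical complication rates were similar between the two (2.1% vs 4.4"%) or 9% (Risks, burr hole).
- Totals of 200 embolized patients and 400 controls (Participants). The size of Group 2 is not given; an even split, 100 against 200, is assumed, with 50/100 and 150/300 as a range.
- Also assumed: independent risks, and controls counted from their surgery.

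**Step 1. What the test sees if Group 2 is counted from embolization: e against s**
- 2.1 − 4.4 = −2.3 points.
- 2.1 − 9.0 = −6.9 points.

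Both favour embolization.

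**Step 2. What a shared start before evacuation gives: s + e − s·e against s**
- 0.044 + 0.021 − 0.044 × 0.021 = 6.41%, against 4.4%: +2.01 points.
- 0.09 + 0.021 − 0.09 × 0.021 = 10.91%, against 9.0%: +1.91 points.

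Both are against embolization, so the sign reverses at either surgical rate.

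**Step 3. Chance that the planned t-test gives p < 0.05 in favour of embolization** (exact binomial enumeration, counted from embolization)

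| Group 2 / controls | s = 4.4% | s = 9% |
|---|---|---|
| 50 / 100 | 2.6% | 31.4% |
| 100 / 200 | 12.8% | 66.7% |
| 150 / 300 | 20.2% | 86.7% |

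With a shared start at 100/200 the chances are 0.3% and 0.5%. As an example at s = 9%, 2/100 against 18/200 gives p = 0.022; with a shared start, 11/100 against 18/200 gives p = 0.58.

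**Step 4. If only part of the controls' evacuation harm is counted.** Suppose half is, as might happen if controls are indexed after their first surgery and only some are re-operated.
- s = 9%: 2.1 − 4.5 = −2.4 points, with a 14% chance of significance at 100/200.
- s = 4.4%: 2.1 − 2.2 = −0.1 points, essentially nothing.

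**Step 5. If embolization avoids repeat surgery.** Participants expects 20% needing surgery without embolization and 5% with it, which is 15 points fewer operations.
- s = 9%: 0.15 × 9 = 1.35 points of harm avoided; the shared-start excess falls from 1.91 to about 0.6.
- s = 4.4%: 0.15 × 4.4 = 0.66 points avoided; the excess falls from 2.01 to 1.35.
- If embolization risk were zero, the shared-start difference would be −1.35 or −0.66 points, with no reversal of sign.

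**The case against.** **The controls' start is not stated.** Specific Aim 2 describes patients with residual hematoma, or recurrence within 30 days of a first operation, and compares them with historical patients who were observed or re-operated. If controls are indexed there, first-evacuation harm is excluded on both sides and only repeat evacuation is asymmetric. This stands, and it limits the size (step 4). It does not settle the matter, because no section assigns that index date.

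**Embolization need not raise total harm.** A reader might infer that an added procedure can only add risk. The document does not support that: Aim 2 expects fewer repeat operations, and Risks cites a 60-embolization series and a review of 193 procedures, both with no procedure-related complications. This also stands (step 5). Moreover, nothing shows that 2.1% is the pure increment from embolization; if some of those patients were also evacuated, adding the two rates counts some harm twice.

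**New deficits may be judged from presentation.** A reader might infer that this endpoint is also measured from the pre-embolization exam. The follow-up schedule and the NIHSS sentence point that way, but the data form records presenting symptoms and NIHSS at presentation. For a patient evacuated and embolized in one stay, presentation precedes evacuation, and an evacuation deficit would then count. The choice is open, so bias is not shown.

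**Evacuation harm may be caught or screened elsewhere.** Adverse events are collected during participation, and consent may be sought when treatment is decided, so some evacuation harm could be recorded. Group 2 also admits patients whose surgery failed at any earlier point, and no comparison of adverse events with controls is planned. Participants adds: "Any patient requiring emergent intervention or experiencing sudden neurologic deterioration is excluded from this study". Whether that removes patients harmed by evacuation depends on when they enrol, so it cannot be counted as an established second source of bias.

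**Conclusion.** The point holds for complications. As the plan most naturally reads, Group 2 is counted from embolization and compared with controls whose complications can come only from surgery, so the comparison is not like for like and can favour embolization. In the illustration, the test sees a difference of 2.3 or 6.9 points in favour of embolization where a shared start shows about 2 points against it.

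Those figures rest on independent risks, controls counted from surgery, 2.1% as the increment from embolization, and no repeat surgery avoided. The probabilities also rest on an assumed Group 2 size. Relaxing these shrinks the distortion, and at the lower surgical rate it can almost vanish. The text therefore supports a comparison that can mislead in a known direction; it does not support the stronger claim that the direction of the safety result will reverse. For new deficits, the finding is only that the reference exam is missing.

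This should be corrected before control charts are abstracted. Confidence is medium.

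**What to change.** Add to Statistical Analysis, for Group 2 and its surgical controls:

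- **Start.** Count from just before the index evacuation in both groups. In Group 2 this is the most recent evacuation before embolization; in controls, the corresponding evacuation.
- **Window.** Count all evacuation and embolization complications from that point over follow-up of equal length. One workable choice is the embolized patient's evacuation-to-embolization interval plus 90 days, applied to the matched controls as well.
- **New deficit.** Define it as a deficit absent at the last exam before that evacuation.
- **Reporting.** Give complications by procedure (evacuation, embolization, any later surgery) in each group, and the overall risk difference with a 95% CI.

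The cost is a short definition and a little more chart review. Date of surgery and time to embolization are already collected under Data Points. Some patients evacuated before enrolment may lack a pre-evacuation exam, and their number should be reported. The embolized group's complication rate will look less favourable than under counting from embolization. One difference remains: Group 2 patients must reach embolization without sudden deterioration, so the report should say how many were consented before evacuation.

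### Both primary endpoints compare physician-selected embolized patients with historical controls by an unadjusted t-test, and the matching that should protect the comparison is not defined

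*Combined protocol and SAP*

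**What the plan says.** **Assignment.** Under Participants, embolization "will be offered in addition to the standard surgical evacuation or observation by the physician in consideration of" each patient's history and present state. There is no randomisation.

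**Controls.** The Objective compares "these two groups of patients who undergo middle meningeal artery embolization to matched historical controls from the past four years". Specific Aim 1 states: "Patients who prospectively undergo middle meningeal artery embolization will be compared to retrospective matched controls". The sample-size paragraph adds "an additional 400 historical matched controls obtained via retrospective chart review from January 1st 2014 to December 31st 2018". Nowhere do the documents name a matching variable, a matching method or a balance check. A 1:2 ratio is only implied, by 200 embolized patients and 400 controls.

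**Who is embolized.** Group 1 takes patients with minimal symptoms "or who are poor surgical candidates (dual antiplatelet therapy or systemic anticoagulation, ASA Class 4 or greater"). Study Procedure says that patients who also have surgery may already have had several evacuations.

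**Aim 2.** The aim is framed thus: "For patients with a residual SDH or who develop recurrent SDH within 30 days of initial standard of care surgery", those given embolization "will be compared to historical patients that are managed with continued observation versus repeat surgery". The Groups list instead admits failure of surgery at any time, with a surgery-alone historical cohort.

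**Analysis.** The two primary endpoints are recurrent or progressive SDH and secondary surgical evacuation, both yes/no. The Statistical Analysis section says: "These primary endpoints will be compared with simple t-test". It mentions no covariate, stratum, weight or sensitivity analysis. Data Points lists baseline variables but does not tie them to matching or adjustment.

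**The concern.** In a non-randomised comparison, a crude difference in event rates mixes the treatment effect with differences in who was treated. Here the main guard against that is matching that cannot be reproduced or audited as written. If candidacy, antithrombotic use, hematoma size or number of earlier evacuations still differs after matching, the t-test carries the difference straight into both primary results, and nothing planned would show that it had.

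The documents make imbalance plausible. Group 1 is partly defined by antithrombotic therapy and ASA class, Group 2 may include repeat evacuations, and no statement says that controls are balanced on these. The Risks section, citing a meta-analysis of earlier studies, notes that more of the embolized patients there stayed on anticoagulants.

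The direction is open. A factor that raises recurrence and is commoner among embolized patients works against embolization. Poor surgical candidacy could lower the chance of being operated on, which would favour embolization on the surgery endpoint. Both mechanisms are assumptions; the documents settle neither.

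**Working it through.** The plan gives no figure for residual imbalance, so there is none to reproduce. Its sample size of 124 does not enter this check. What follows is an illustration.

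**Inputs from the sample-size paragraph:** control rate 20%; embolization rate 5% (power check only).

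**Assumed inputs:**
- Two-sided alpha 0.05. The documents print 0.5, which looks like a typing error.
- 100 versus 200 patients per aim. The plan gives 200 and 400 with no split between aims.
- One binary prognostic factor, present in 60% of embolized patients and in a share s0 of controls, with event-rate ratio RR of 0.5, 1.5 or 2.
- No true treatment effect, except in the power check.

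**Step 1. Embolized event rate under no effect**

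p1 = 20% × (1 − 0.6 + 0.6·RR) / (1 − s0 + s0·RR)

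Example, s0 = 40% and RR = 0.5: 20% × 0.70 / 0.80 = 17.50%, a bias of −2.5 points (negative favours embolization).

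**Step 2. Rejection rate of the crude equal-variance t-test**, by exact binomial enumeration

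| Factor, embolized / control | RR | p1 | Bias (points) | Rejects, total | For embolization | Against |
|---|---|---|---|---|---|---|
| 60 / 60 | any | 20.00% | 0 | 4.9% | 2.3% | 2.6% |
| 60 / 50 | 0.5 | 18.67% | −1.3 | 5.6% | 4.3% | 1.3% |
| 60 / 50 | 1.5 | 20.80% | +0.8 | 5.4% | 1.6% | 3.8% |
| 60 / 50 | 2 | 21.33% | +1.3 | 6.0% | 1.2% | 4.7% |
| 60 / 40 | 0.5 | 17.50% | −2.5 | 7.6% | 6.9% | 0.7% |
| 60 / 40 | 1.5 | 21.67% | +1.7 | 6.5% | 1.0% | 5.4% |
| 60 / 40 | 2 | 22.86% | +2.9 | 9.1% | 0.6% | 8.6% |
| 60 / 20 | 0.5 | 15.56% | −4.4 | 14.5% | 14.4% | 0.2% |
| 60 / 20 | 1.5 | 23.64% | +3.6 | 11.5% | 0.4% | 11.2% |
| 60 / 20 | 2 | 26.67% | +6.7 | 26.0% | 0.1% | 26.0% |

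Parts may not sum exactly because of rounding. At 200 versus 400, the 60/20 totals become 25.5%, 18.1% and 45.6%: a larger sample makes a biased difference more likely to be significant.

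**Step 3. Power at the planned effect.** With 5% versus 20% at 100 versus 200, power is 96.9%. The worst factor above multiplies the embolized rate by 26.67/20 = 1.333. If the treatment rate ratio is constant, 5% becomes 6.67% and power is 89.7%.

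**Step 4. Does the t-test itself matter?** An uncorrected chi-square gives 5.0% at balance against 4.9%, and 14.6%, 11.8% and 26.5% at 60/20 against 14.5%, 11.5% and 26.0%. It hardly matters.

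**Step 5. What adjustment can recover.** Standardise controls to the recorded factor mix of the embolized patients, with 90% sensitivity and specificity of recording. For 60/40 and RR 0.5:
- Recorded share: embolized 0.6×0.9 + 0.4×0.1 = 0.58; controls 0.4×0.9 + 0.6×0.1 = 0.42.
- Control rate without the factor: 0.20/0.80 = 25%.
- Control rate if recorded present: 25% × (1 − 0.5×0.36/0.42) = 14.29%; if recorded absent: 25% × (1 − 0.5×0.04/0.58) = 24.14%.
- Standardised control rate: 0.58×14.29% + 0.42×24.14% = 18.42%.
- Remaining bias: 17.50 − 18.42 = −0.9 points, from −2.5.

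At 60/20 the bias falls from −4.4 to −2.1. Adjustment helps only as far as the factor is measured.

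**The case against.** The case against rests mainly on size. The documents do say that the controls are matched and give no factor shares or effects, so every error rate above is assumed. With modest residual imbalance (60/50), total error is 5.4–6.0% against 4.9%, which is small. The large figures need near-absent matching on a strong factor. False claims in favour of embolization exceed the balanced 2.3% only at ratio 0.5; at ratios above 1 the test is conservative for efficacy. The planned effect survives. All of this stands, and it limits how serious the point is.

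It is also fair that matching is not the only protection. Each aim has its own comparator, which keeps medically managed patients apart from surgical ones. That is partial protection: it does nothing about differences within a comparator group.

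What does not stand is the reply that the word matched already covers it. Without variables or a balance report, a reader could not tell a 60/60 comparison from a 60/20 one, and the stated analysis would treat them alike.

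**Conclusion.** The point holds as a cheap improvement. For both primary endpoints, the stated test leaves in the result any imbalance that an undefined matching step fails to remove. On the assumptions listed, the cost ranges from negligible (5.4–6.0% total rejection at 60/50) through 6.5–9.1% (60/40) to 11.5–26.0% (60/20, close to no matching on the factor). Power at the planned effect stays at about 90% or more, given a constant rate ratio. The point matters most if the true effect is small.

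A reader might infer more than the documents support:
- *That the design is biased in favour of embolization.* The direction is unknown, and the 26.0% figure is essentially all against it.
- *That the controls are unmatched.* They are said to be matched; what is missing is how.
- *That using a t-test on a yes/no outcome is the fault.* It gives nearly the same answer as chi-square.

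The two descriptions of the Aim 2 population and comparator are a separate consistency point and add no weight to this one.

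**What to change.** 1. **Before any control chart is reviewed**, name the matching variables. Aim 1: age, antithrombotic use, ASA class or surgical candidacy, SDH size. Aim 2: age, antithrombotic use, SDH size, number of prior evacuations. Within each aim, match two controls to each embolized patient on a propensity score built from these, and report standardised differences after matching.

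2. **In Statistical Analysis**, replace the t-test for the primary endpoints with:

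> *For each aim, the risk difference in the matched sample, standardised to the embolized patients, will be estimated from a logistic regression with treatment and the matching variables, with a 95% CI from standard errors clustered on matched set.*

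3. **Leave calendar year out of the score.** Controls end in December 2018 and the protocol is dated June 2020, so year separates the groups completely. State the period difference and unmeasured confounding as limitations.

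4. **Separately**, reconcile Specific Aim 2 with the Groups list on the Aim 2 population and comparator before controls are selected.

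**Cost.** Mostly wording and programming. Age, antithrombotic use and SDH size are already collected for embolized patients. ASA class or candidacy and number of prior evacuations need columns of their own. The variables must be abstracted for up to 400 controls, and for the wider pool they are chosen from: matching 200 patients two to one from exactly 400 charts would use every chart. A rule for missing baseline values is needed. Some precision may be lost. With one perfectly recorded factor, 200,000 simulated trials changed the SD of the estimate by between −2% (4.65 against 4.74 points, 60/40, RR 0.5) and +22% (6.40 against 5.25, 60/20, RR 2). The loss for the full variable set was not computed and would be larger where overlap is poor.
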